8.4.3.6. Physical Examination

Physical examination will consist of complete and routine examinations:

Complete physical examination will include abdominal, cardiovascular, general appearance, head, eyes, ears/nose/throat, lymph nodes, musculoskeletal, neck, neurological, dermatological, and respiratory.

Routine physical examinations will include abdominal, cardiovascular, general appearance, respiratory, neurological, and other.

The complete examination will be performed at Day 1 and week 96 and the routine examination will be performed at weeks 12, 24, 48 and 72.

If any significant abnormality started prior to informed consent, it will be record in corresponding medical history. If any significant abnormality started after informed consent, it will be record corresponding event on AE form.

8.4.3.7. Body Weight

Body weight will be measured and recorded in pounds or kilograms.

8.5. Analysis Visit Definitions

The acceptable visit dates windows of observation, examination, and investigation are specified as in Table 5 : The analysis visit windows. Data obtained within the acceptable windows will be used for analysis or presentation. If the dates of observation, examination, or investigation are out of the following acceptable range, data obtained on those days will not be used for analysis or summary statistics. However, all data as captured will be listed.

If there are multiple data in a window, the closest data to nominal day will be used. If the distance to the nominal day is the same, the data of later date will be used.

Table 5: The analysis visit windows

| Analysis visit | Nominal day | Window |
|----------------|-------------|----------------|
| Baseline | Day 1 | NA |
| Week 12 | Day 85 | Day 2 to 127 |
| Week 24 | Day 169 | Day 128 to 253 |
| Week 48 | Day 337 | Day 254 to 421 |
| Week 72 | Day 505 | Day 422 to 589 |
| Week 96 | Day 673 | Day 590 to 701 |

In case assessments are done at the Early Termination visit, these assessments will be used as data for the scheduled visit closest to the early termination time point, in case the corresponding data are missing from this visit.

Statistical Analysis Plan
Protocol No. MT-1186-A03

Mitsubishi Tanabe Pharma America, Inc.

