#### **17.3.2.2 Handling of Time Point Data in Analyses Performed by Measurement time Point (Analysis Visit Windows)**

For the analyses performed for each measurement time point, the allowable range of data handling for the analysis will be specified as analysis visit window in the SAPs.

No data imputation will be performed using data from outside the allowable range. If multiple values are available within the allowable range for the endpoint in question, then the latest value will be analyzed.

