2. INTRODUCTION

This statistical analysis plan (SAP) is based on the final global protocol amendment (v3.0) dated 27-July-2021 and country specific (v3.2) for Japan dates 22-September-2022. The plan covers statistical analysis, tabulations and listings of the study data to investigate the long-term safety and tolerability of oral edaravone in subjects with ALS over 96 weeks.

The structure and content of this SAP provides sufficient details to meet the requirements identified by the FDA and International Conference on Harmonization of Technical Requirements for Registration of Pharmaceuticals for Human Use (ICH): E9 Guidance on Statistical Principles in Clinical Trials. All work planned and reported for this SAP will follow internationally accepted guidelines, published by the American Statistical Association, and the Royal Statistical Society, for statistical practice.

The following documents were reviewed in preparation of this SAP:

- Clinical Study Protocol MT-1186-A03 Version 3.0 issued on, 27-July-2021
- Case report form (CRF) for MT-1186-A03
- ICH E9 Guidance on Statistical Principles for Clinical Trials.

- ICH E3 Structure and Content of Clinical Study Reports (CSRs)
- ICH E14 (may, 2005) clinical evaluation of QT/QTC interval prolongation

Any statistical analysis details described in this document supersede the description of statistical analysis in the protocol. In case of major differences, e.g. changes in the analysis related to the primary endpoint, a protocol amendment will be considered. The SAP may be updated during the study conduct and will be finalized before final database lock. Any deviations from the planned analysis will be described and justified in the CSR.

The analyses related to the primary and exploratory objectives will be performed when all subjects complete 96 weeks of treatment or until the drug is commercially available in that Country.

Database lock will be associated with the current designated SAP that will describe the analysis up to Week 96 and will be approved and signed prior to the database lock. The analysis results over 96 weeks will be used for the CSR to support publications and marketing activities.

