9.2.1. Efficacy Endpoints

For the efficacy endpoints, continuous data will be summarized at each analysis visit using summary statistics. Absolute values and changes from baseline will be presented. All categorical endpoints will be summarized at each analysis visit, using frequency tabulations. As the primary purpose of this study is to explore the safety of edaravone and not to perform confirmatory analyses, there will be no formal hypothesis testing performed and adjustments for multiplicity are not required.

9.2.1.1. ALSFRS-R change from baseline up to Week 96

The ALSFRS-R score of each item, domain score and total score will be listed. The total ALSFRS-R score and change from baseline to each post baseline visit up to week 96 will be plotted by visit. This analysis will be made on the safety analysis population.

The changes from baseline to (CHG) all post-baseline visits until week 96 in ALSFRS-R will be estimated using a Mixed Model for Repeated Measures (MMRM). The model includes response data from all post-baseline visits with no imputation for missing data. The ALSFRS-R at baseline (BASE), concomitant riluzole (RI) and visit (AVISIT) at week 24, 48, 72 and 96 will be included as fixed factors in the model. An unstructured covariance structure will be assumed and the denominator degrees of freedom will be computed using the Kenward-Roger method. In case the model will not converge with the unstructured covariance structure, the heterogeneous Toeplitz structure (TOEPH), Heterogeneous Autoregressive(1) (ARH(1)) , the heterogeneous compound symmetry (CSH), Toeplitz (TOEP), First-order autoregressive (AR(1)), and Compound symmetry (CS) will be used instead (in that order). The changes from baseline and their associated 95% Confidence Limits will be estimated, separately for each visit, from the same MMRM using LSMEANS estimates.

The SAS code planned for the analysis is outlined below.

[REDACTED]

For subgroup analysis, the above MMRM model will be employed using the corresponding subgroup categorical variable and the interaction between the subgroup and visit.

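### SAP 8.5 counts early-termination ALSFRS-R scores at visits up to 83 days later and leaves roughly 40 to 65% of them unused, so Week 96 decline is likely to be somewhat understated

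*SAP*

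**What the plan says.** - **ET data.** SAP 8.5 gives an ET assessment to the scheduled visit nearest in time, "in case the corresponding data are missing from this visit". Protocol 10.1.3 places the ET assessment within 7 days of leaving.
- **Several values in a window.** SAP 8.5: "If there are multiple data in a window, the closest data to nominal day will be used", with the later date winning a tie. Protocol 17.3.2.2 has a different rule: "then the latest value will be analyzed".
- **Windows (SAP Table 5).** The first post-baseline row reads "Week 12 | Day 85 | Day 2 to 127". The windows after it are Days 128 to 253 for Week 24 (nominal Day 169), Days 254 to 421 for Week 48 (nominal Day 337), Days 422 to 589 for Week 72 (nominal Day 505) and Days 590 to 701 for Week 96 (nominal Day 673).
- **Model.** The visit factor in SAP 9.2.1.1 has four levels, Weeks 24, 48, 72 and 96. "The model includes response data from all post-baseline visits with no imputation for missing data". SAP 10.3 reports efficacy at baseline and those four visits, so Week 12 has no place in the efficacy analysis.
- **Precedence.** SAP section 2: "Any statistical analysis details described in this document supersede the description of statistical analysis in the protocol". SAP section 11, on changes from the protocol, lists only the physical examination summary.

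**The concern.** The ET score is the last functional measurement on a subject who leaves. Protocol 9.6 ties several reasons for withdrawal to progression: tracheostomy, permanent ventilation and worsening of the disease. An MMRM without imputation relies on the observed scores to carry information about the missing ones.

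SAP 8.5 handles the ET score poorly in two ways. If it is used, it is treated as if it had been taken at the nominal visit, although it may have been taken weeks earlier and, in a declining disease, is then too high for that visit. If the nearest visit is filled, or the score falls in the Week 12 window, it is listed but not modelled.

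At stake is the estimated ALSFRS-R change at Week 96. The SAP says the 96-week results will support publications and marketing.

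**Working it through.** The plan states no figure for ET scores used or lost, and no dropout rate or timing, so there is nothing to reproduce. The Table 5 limits can be checked as midpoints of nominal days: (85+169)/2 = 127, (169+337)/2 = 253, (337+505)/2 = 421, (505+673)/2 = 589. All match, so closest visit and window agree.

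**1. Which ET days are used.** Take ET Days 2 to 672 (671 days) and assume earlier scheduled visits were attended on their nominal day.

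- Week 12 window: Days 2–127 = 126 days, 126/671 = 18.8%.
- Nearest visit already filled: Days 169–253, 337–421 and 505–589 = 3 × 85 = 255 days, 255/671 = 38.0%. Leaving out the three nominal days gives 252, 37.6%.
- Used: Days 128–168, 254–336, 422–504 and 590–672 = 41 + 3 × 83 = 290 days, 43.2%.

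Under even timing, 126 + 255 = 381 days (56.8%) are unused. Other assumed timings:

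| Dropout timing | Nearest visit filled | Week 12 window | Total unused |
|---|---|---|---|
| Even | 38.0% | 18.8% | 56.8% |
| Constant hazard, 30% leaving | 37.1% | 21.6% | 58.7% |
| Constant hazard, 60% leaving | 35.3% | 26.3% | 61.6% |
| Rising, linear | 42.7% | 3.6% | 46.3% |
| Rising, quadratic | 41.0% | 0.7% | 41.7% |
| Falling, linear | 33.6% | 32.9% | 66.5% |
| Only after Week 24 | 50.5% | 0% | 50.5% |

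If closest visit means ALSFRS-R visits only, even timing gives 38% unused, or 50% if baseline counts as a visit. If the Week 36, 60 and 94 contacts count too, it is about 80%.

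**2. How far used scores are moved.** The maximum is 673 − 590 = 83 days (also 337 − 254 and 505 − 422); for Week 24 it is 169 − 128 = 41. Under even timing the mean is (861 + 3 × 3,486)/290 = 39.0 days, where 861 = 41 × 42/2 and 3,486 = 83 × 84/2. At an assumed 1 point per month, that is 39.0/30.4 = 1.3 points per used score.

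**3. Effect on the Week 96 estimate.** Assumed: mean slope −1 point per month, slope SD 0.6, linear decline; maximum likelihood for monotone missing data stands in for the MMRM. Error = estimate minus truth; positive means decline is understated.

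Simulation A (200,000 subjects per setting, truth −22.35):

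| Dropout | Leaving early | SAP rule | No ET data | Difference |
|---|---|---|---|---|
| Unrelated | 28% | 0.24 | 0.00 | 0.24 |
| Unrelated | 63% | 0.70 | 0.01 | 0.69 |
| Score-driven | 57% | 1.45 | 0.77 | 0.68 |
| Score-driven | 76% | 2.59 | 1.58 | 1.01 |
| Slope-driven | 32% | 1.28 | 1.16 | 0.12 |
| Slope-driven | 57% | 2.79 | 2.58 | 0.21 |
| Score-driven, rising | 58% | 1.84 | 1.12 | 0.72 |
| Score-driven, rising | 73% | 3.05 | 2.19 | 0.86 |

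Simulation B (60,000 subjects per setting, residual SD 1.5, truth −22.08):

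| Dropout | Leaving early | SAP rule | No ET data | Random slope, all scores | Random slope, no ET |
|---|---|---|---|---|---|
| Unrelated | 29% | 0.26 | 0.00 | 0.01 | 0.00 |
| Unrelated | 62% | 0.68 | 0.01 | −0.05 | −0.01 |
| Loss-driven | 59% | 1.53 | 0.88 | 0.31 | 0.64 |
| Loss-driven | 68% | 1.98 | 1.21 | 0.37 | 0.83 |
| Loss-driven | 82% | 3.17 | 2.27 | 0.55 | 1.28 |

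Trials of 140 subjects (60 per setting, 55 to 76% leaving) gave 1.21, 1.77 and 2.33 for the planned MMRM. A further set gave 0.3 to 0.8 (unrelated) and 2.0 to 3.1 (progression-driven). One separate progression-driven setting reached 3.67 (2.93 with no ET data).

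**4. Attribution.** The SAP rule and the no-ET analysis both lack the discarded scores; they differ only in the late-dated scores that the SAP adds. The difference column is therefore the error from late dating, and the no-ET column is what dropout alone produces. The discarded scores do hold information: at their actual days, ET scores roughly halve the random-slope error under loss-driven dropout (0.64 to 0.31; 1.28 to 0.55).

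**The case against.** **Size of the loss.** A reader might infer that the missing-only clause throws away more than half of ET scores. It does not: under even timing it covers about 38% of days. The total passes half only by adding the Week 12 window, a separate route, and by assuming flat or early dropout; with rising dropout it is 42 to 46%. This objection stands.

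**Cause.** A reader might also infer that decline is understated because scores are discarded. With dropout unrelated to outcome, discarding every ET score leaves the estimate unbiased (errors 0.00 and 0.01), while the SAP rule does not. Under progression-driven dropout much of the error remains with no ET data. This also stands: the full 1.2 to 3.2 points cannot be charged to the rule.

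**Dropout need not follow progression.** Protocol 10.1.2 ends treatment when the drug becomes commercially available in a country, an administrative exit. If that dominates, the error is nearer 0.2 to 0.8 points. Fair.

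**A straight-line model is no safe replacement.** Its small errors in Simulation B are partly built in, because the data were generated as straight lines. With modest curvature (time to the power 0.7 or 1.4) its Week 96 error was 2.2 to 6.1 points against 0.4 to 3.9 for the planned MMRM, and larger in all six settings. Other curved runs gave 0.8 to 3.5. Adding curvature to the mean brought errors to 1.2 points or less, below the SAP rule in every setting run.

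**Consequence.** The endpoint is exploratory, single-arm and untested, and all scores are listed. That limits the priority, but a listing does not correct an estimate.

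**Conclusion.** The point holds in this form. SAP 8.5 can count an ET ALSFRS-R score at a visit up to 83 days later, and leaves roughly 40 to 65% of ET scores out of the model under the Table 5 windows. In every setting run the rule understated Week 96 decline, and where the two were compared it did worse than using no ET data at all. The size is about 0.2 to 0.8 of 22 points if dropout is unrelated to outcome and about 1.2 to 3.2 if it follows progression, with one run at 3.7. The rule's own share comes mainly from late-dated scores (0.1 to 1.0 points in Simulation A).

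All slopes, dropout rates and timings are assumptions. The documents establish the rule and the windows, but not the share lost or the bias. The change from the protocol's latest-value rule is within the SAP's authority, but SAP section 11 does not list it.

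**What to change.** 1. Keep the MMRM. Add one supplementary mixed model on actual study day using every ALSFRS-R total, including ET and unscheduled scores, with random intercept and slope and a non-linear mean (for example linear plus quadratic day). Report change at Days 169, 337, 505 and 673 with 95% CI beside the MMRM.
2. Report the MMRM once more with ET scores not moved to a later visit, or moved only when close to the nominal day. The ±7-day visit window in Protocol Table 1 is one possible limit.
3. In SAP 8.5, state which visits count as scheduled for ALSFRS-R. In SAP section 11, list the departure from Protocol 17.3.2.2.

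Returning to the latest-value rule would not be enough. It cuts the unused share under even timing to 126/671 = 18.8%, but it dates some scores too early and can overstate earlier decline (Simulation A, unrelated dropout, 63% leaving: −17.00 at Week 72 against a true −16.77).

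The cost is a little more analysis work on data already collected, and reliance on an assumed trajectory shape, which is why the MMRM stays. SAP section 2 allows updates before final database lock.

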8.6. Cycle Definition

The cycles definition during MT-1186-A03 are specified in Table 6: Cycle definition. The date of the first dose of study drug in this study is defined as Day 1. The cycles have no time window definition. Differences between dosing cycles and analysis cycles may occur but will not be considered.

Table 6: Cycle definition

| Cycle | Day |
|--------------|------------------|
| Cycle 1 | Day 1 to 28 |
| Cycle 2 | Day 29 to 56 |
| Cycle 3 | Day 57 to 84 |
| Cycle 4 | Day 85 to 112 |
| Cycle 5 | Day 113 to 140 |
| Cycle 6 | Day 141 to 168 |
| Cycle 7 | Day 169 to 196 |
| Cycle 8 | Day 197 to 224 |
| Cycle 9 | Day 225 to 252 |
| Cycle 10 | Day 253 to 280 |
| Cycle 11 | Day 281 to 308 |
| Cycle 12 | Day 309 to 336 |
| Cycle 13 | Day 337 to 364 |
| Cycle 14 | Day 365 to 392 |
| Cycle 15 | Day 393 to 420 |
| Cycle 16 | Day 421 to 448 |
| Cycle 17 | Day 449 to 476 |
| Cycle 18 | Day 477 to 504 |
| Cycle 19 | Day 505 to 532 |
| Cycle 20 | Day 533 to 560 |
| Cycle 21 | Day 561 to 588 |
| Cycle 22 | Day 589 to 616 |
| Cycle 23 | Day 617 to 644 |
| Cycle 24 | Day 645 on later |

9. STATISTICAL METHODOLOGY

9.1. Study Subjects

9.1.1. Subject Disposition

Subject disposition will be listed and summarized using descriptive statistics. The percentages will be calculated based on the number of enrolled subjects, unless otherwise specified.

- The number of subjects enrolled in MT-1186-A01
- The number (%) of subjects in the full analysis set (% calculated from the number of enrolled subjects in MT-1186-A01)
- The number (%) of subjects who discontinued in MT-1186-A01 (% calculated from the number of enrolled subjects in MT-1186-A01)
- The number (%) of subjects completed MT-1186-A01 (% calculated from the number of enrolled subjects in MT-1186-A01)
- The number of subjects screened for MT-1186-A03
- The number (%) of subjects who failed screening, including the distribution of reasons for screen failure (% calculated from the number of screened subjects in MT-1186-A03)
- The number (%) of subjects enrolled in MT-1186-A03 (% calculated from the number of screened subjects in MT-1186-A03)
- The number (%) of subjects in the safety analysis population
- The number (%) of subjects who completed MT-1186-A03 (% calculated from the number of enrolled subjects in MT-1186-A03)
- The number (%) of subjects who discontinued in MT-1186-A03 including the distribution of reasons for discontinuation (% calculated from the number of enrolled subjects in MT-1186-A03)

9.1.2. Protocol Deviations

Protocol Deviation which collected in MT-1186-A03 will be listed and the major protocol deviations will be summarized for the safety analysis population.

9.1.3. Demographic and Other Baseline Characteristics

Demographics and baseline characteristics will be listed and summarized descriptively for safety analysis population. All parameters described in Table 3: Demographic and Baseline Characteristics will be used for the analysis.

9.1.4. ALS History

ALS History will be listed and summarized descriptively for safety analysis population. All parameters described in Table 4: ALS History Parameters

9.1.5. Concomitant Medications

All concomitant medication will be summarized and listed for the safety analysis population. The summary will be presented in tabular form using the ATC Level 1, ATC Level 2, and Preferred Term (PT). Frequencies and percentages of subjects receiving medications will be presented. Separate summaries of permitted ALS Treatment concomitant medications (Riluzole, AMX0035), will be presented in tabular form using the ATC Level 4 and preferred term. The tables will be sorted by overall descending frequency of ATC Level(s) and then, within an ATC Level, by overall descending frequency of PT.

Concomitant medication will be listed for subjects that had platelet count ≤ 100000 (/mm³) at any post baseline for the safety analysis population.

9.1.6. Study Medication Exposure and Compliance

Study medication exposure during MT-1186-A03 will be calculated as specified in section 8.4.1.4. The following information will be summarized and listed for the safety analysis population:

- The number of subjects exposed to study treatment
- The number of subjects exposed to study treatment by oral administration
- The number of subjects exposed to study treatment by PEG/RIG administration
- Duration of exposure of study treatment (days) by Cycle and Total
- Total duration of exposure to study treatment, expressed as person years (sum of exposure to study treatment)
- Total duration of exposure (days) under PEG/RIG administration
- Time to date subjects switched to PEG/RIG administration

Treatment compliance will be determined by performing study treatment accountability of returned study treatment used and unused according to section 8.4.1.4. Treatment compliance will be summarized and listed for the safety analysis population using descriptive statistics. Non-compliance is defined as taking $< 80\%$ or $> 120\%$ of study medication during evaluation periods. The proportions of subjects with non-compliance as defined above will be summarized and listed for the safety analysis population.

9.2. Efficacy Analysis

In general, efficacy analyses will be made on the safety analysis population.

9.2.1. Efficacy Endpoints

For the efficacy endpoints, continuous data will be summarized at each analysis visit using summary statistics. Absolute values and changes from baseline will be presented. All categorical endpoints will be summarized at each analysis visit, using frequency tabulations. As the primary purpose of this study is to explore the safety of edaravone and not to perform confirmatory analyses, there will be no formal hypothesis testing performed and adjustments for multiplicity are not required.

9.2.1.1. ALSFRS-R change from baseline up to Week 96

The ALSFRS-R score of each item, domain score and total score will be listed. The total ALSFRS-R score and change from baseline to each post baseline visit up to week 96 will be plotted by visit. This analysis will be made on the safety analysis population.

The changes from baseline to (CHG) all post-baseline visits until week 96 in ALSFRS-R will be estimated using a Mixed Model for Repeated Measures (MMRM). The model includes response data from all post-baseline visits with no imputation for missing data. The ALSFRS-R at baseline (BASE), concomitant riluzole (RI) and visit (AVISIT) at week 24, 48, 72 and 96 will be included as fixed factors in the model. An unstructured covariance structure will be assumed and the denominator degrees of freedom will be computed using the Kenward-Roger method. In case the model will not converge with the unstructured covariance structure, the heterogeneous Toeplitz structure (TOEPH), Heterogeneous Autoregressive(1) (ARH(1)) , the heterogeneous compound symmetry (CSH), Toeplitz (TOEP), First-order autoregressive (AR(1)), and Compound symmetry (CS) will be used instead (in that order). The changes from baseline and their associated 95% Confidence Limits will be estimated, separately for each visit, from the same MMRM using LSMEANS estimates.

The SAS code planned for the analysis is outlined below.

[REDACTED]

For subgroup analysis, the above MMRM model will be employed using the corresponding subgroup categorical variable and the interaction between the subgroup and visit.

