## **9.6 Withdrawal of Individual Subjects**

A subject will be withdrawn from the study if the subject meets any of the following criteria:

- Requests to be withdrawn from the study;
- Has been found to be ineligible for participation in the study;
- The investigator (or subinvestigator) concludes that a subject should be withdrawn if continuation in the study is difficult due to AEs (e.g., hypersensitivity reactions);
- Is pregnant;
- Requires tracheostomy;
- Requires permanent assisted mechanical ventilation ( $\geq 23$  hours/day);
- The investigator (or subinvestigator) judges' continuation of the study to be inappropriate due to exacerbation of the primary disease;
- Development of significant liver dysfunction:
  - ALT or AST greater than 8 times the ULN;
  - Persistent ALT or AST of greater than 5 times the ULN for at least 2 weeks;
  - ALT or AST greater than 3 times the ULN AND elevated total bilirubin greater than 2 times ULN;
  - Symptoms consistent with liver dysfunction (e.g., fatigue, nausea, vomiting, abdominal pain/tenderness, fever, rash, eosinophilia  $>5\%$ ) with concomitant ALT or AST greater than 3 times the ULN.
- Note: Subjects meeting these criteria do not require withdrawal if alternative etiology is identified on discussion with the Study Medical Monitor.
- Noncompliance (i.e., misses more than 20% of doses in 2 consecutive dosing cycles, after consultation with MTDA or designee).

If a subject is withdrawn prematurely from the study, the date the subject is withdrawn from the study and the reason for withdrawal will be recorded in the electronic case report form (eCRF).

In the event that a subject drops out of the study at any time, the reason for discontinuation must be fully documented in the source documents and the eCRF. The Investigator site personnel will document the AEs and any other assessments in the source documents and will make every effort to complete all required early termination (ET) assessments. Study sites must make all efforts to follow-up with phone calls.

Subjects who are withdrawn from the study following enrollment may not re-enter the study.

The study may be terminated by the Sponsor at any time upon becoming aware of data that could compromise the safety and/or well-being of subjects or for any other reason it deems appropriate.

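### The ALSFRS-R MMRM text lists no baseline-by-visit term; later LS means are biased if the baseline effect changes between visits and dropout depends on baseline score

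*SAP*

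**What the plan says.** SAP section 9.2.1.1 models change in ALSFRS-R with an MMRM. On the mean model it says: "The ALSFRS-R at baseline (BASE), concomitant riluzole (RI) and visit (AVISIT) at week 24, 48, 72 and 96 will be included as fixed factors". The only interaction with visit that it names belongs to the subgroup model, which adds "the interaction between the subgroup and visit"; section 9.4 makes region the subgroup.

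On missing data: "The model includes response data from all post-baseline visits with no imputation for missing data". On covariance: "An unstructured covariance structure will be assumed and the denominator degrees of freedom will be computed using the Kenward-Roger method", with a list of simpler structures if the fit does not converge. The reported quantities are changes from baseline with 95% limits, "separately for each visit, from the same MMRM using LSMEANS estimates". The text does not say at which baseline value the LS means are evaluated.

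The section announces code ("The SAS code planned for the analysis is outlined below"), but the code is redacted, so neither the MODEL nor the LSMEANS statement can be read.

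**The concern.** As the prose stands, a one-point difference in baseline score has the same effect on change at Week 24 as at Week 96. If the rate of decline is related to baseline function, that effect must grow with time, and one coefficient is then a compromise that fits the later visits poorly. While everyone is observed the misfit averages out. Once the subjects still observed differ in baseline from those enrolled, it does not.

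Dropout linked to disease state is foreseeable. Protocol section 9.6 withdraws subjects who need tracheostomy or permanent ventilation, and those for whom the investigator judges "continuation of the study to be inappropriate due to exacerbation of the primary disease". The documents do not tie withdrawal to the baseline score itself.

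The stake is limited but real. There is no comparator, so no between-arm difference exists in which the error could cancel. SAP section 7.2 makes point estimates with 95% confidence intervals the exploratory efficacy output, and SAP section 2 foresees publication and marketing use of the 96-week results.

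**Working it through.** **From the documents.** Fixed terms BASE, RI and AVISIT at four visits; unstructured covariance; no imputation; about 140 subjects (SAP section 4.2). The documents give no SD, decline rate, dropout rate or derived sample size, so there is no plan figure to reproduce.

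**Assumed.** True baseline mean 36, SD 8; decline 1 point per month, SD 0.6; visit noise SD 2; correlation ρ between baseline and rate of decline from 0 to 0.6 in size (negative means that a better baseline goes with slower decline); logistic dropout on baseline, with base-case Week 96 retention of 47% to 55%. True Week 96 change is about −22 points. Riluzole is left out of the simulated model; the mechanism does not need it.

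**Step 1: when the slope changes.** With t months since baseline, the slope of change on observed baseline is

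slope(t) = (−ρ × 8 × 0.6 × t − 2²) / (8² + 2²).

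- ρ = 0: −4/68 = −0.06 at every visit.
- ρ = −0.4, Week 24 (t = 24 × 7/30.44 = 5.52): (10.60 − 4)/68 = 0.10.
- ρ = −0.4, Week 96 (t = 22.08): (42.39 − 4)/68 = 0.56.

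**Step 2: when that matters.** To a first approximation the bias at a visit is (slope at that visit − common slope) × (mean baseline of those still observed − baseline at which the LS mean is taken). Within-subject correlation offsets part of it. The product vanishes if either factor is zero, so both conditions are needed.

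**Step 3: simulation.** Maximum-likelihood MMRM, unstructured covariance, 60,000 to 80,000 subjects. Week 96 bias in points, dropout only after Week 24:

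| ρ | Simulated slope, Week 24 to 96 | As written, LS mean at full-set baseline | Interaction, full-set baseline | Interaction, baseline mean over observed records |
|---|---|---|---|---|
| 0 | −0.06 to −0.05 | −0.02 | −0.02 | −0.10 |
| −0.2 | 0.02 to 0.26 | +0.36 | 0.00 | +0.43 |
| −0.4 | 0.10 to 0.58 | +0.73 | +0.02 | +0.95 |
| −0.6 | 0.18 to 0.88 | +1.12 | +0.03 | +1.44 |
| +0.4 | −0.21 to −0.69 | −0.72 | +0.02 | −1.08 |

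- The ρ = 0 row has dropout that depends strongly on baseline and shows no material bias. With a changing slope but dropout independent of baseline, the bias was −0.01.
- Bias grows with time: for ρ = −0.4 it is 0.00, +0.20, +0.46 and +0.73 at Weeks 24, 48, 72 and 96.
- With dropout before Week 24 as well, the model as written gives +0.70, +1.36 and +2.13 for ρ = −0.2, −0.4 and −0.6. Part of this comes from subjects with no post-baseline score, who add nothing to the fit. Measured against subjects with at least one score, it is +0.24, +0.51 and +0.84.
- In that setting the interaction with LS means at the mean over observed records leaves +0.71 to +2.50. With LS means at the full-set mean, bias in all main settings is −0.08 to +0.06, which is simulation error.
- Milder inputs (n = 140, slope rising from 0.05 to 0.20 or 0.35, 41% to 46% missing at Week 96, 150 trials per setting) give +0.15 to +0.63 as written. The simulation error is about 0.85/√150 = 0.07.

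**Step 4: at n = 140.** Middle early-dropout case, 400 trials: bias +1.41, SD of the estimate 1.45. Approximate coverage of a nominal 95% interval is Φ(1.96 − 1.41/1.45) − Φ(−1.96 − 1.41/1.45) = 0.84. A bias of 0.73 with the same SD gives 0.92. With both parts of the fix, bias is +0.04 and SD 1.51, so root mean squared error falls from √(1.41² + 1.45²) = 2.02 to √(0.04² + 1.51²) = 1.51.

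**The case against.** - **The code may already contain the term.** This stands. The redaction means that the prose supports only a statement about the prose. But the same section spells out a visit interaction where it wants one, so main effects only is the natural reading, and the text should settle the matter.
- **A reader might infer that baseline-dependent dropout by itself biases the later means.** It does not; the ρ = 0 row shows this. The baseline effect must also differ between visits, and the documents give no slope, SD or dropout relation from which to assert that it does.
- **A reader might infer that the plan flatters the drug.** The documents do not support a direction. The error understates decline if lower-function subjects decline faster and leave more often; with the opposite relation to decline it overstates it (−0.72 above).
- **Early-termination data recover some of the loss.** SAP section 8.5 says "these assessments will be used as data for the scheduled visit closest to the early termination time point". This helps but is partial: a subject who leaves by Day 127 falls in the Week 12 window, which is not an MMRM visit, and may still contribute no score.
- **Other presentations exist.** By-visit summaries, plots and listings are planned, and Protocol section 17.3.5.1 specifies descriptive change with a 95% CI. They rest on observed subjects and do not correct for dropout. In a simulated case with 63% retained at Week 96 (ρ = −0.4), the observed-case mean was off by +1.64, against +0.90 for the MMRM as written.
- **The consequence is small.** The endpoint is exploratory and nothing is tested. This stands and sets the weight of the point.

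**Conclusion.** The point holds in conditional form and is a worthwhile refinement. The text lists no baseline-by-visit interaction, and what will be fitted cannot be confirmed. If the baseline effect differs between visits and dropout depends on baseline score, later-visit LS means are biased, and the unstructured covariance does not remove the bias. Under the assumed inputs the Week 96 error is roughly 0.2 to 2 points in either direction. The 0.36 to 2.13 points found against the full enrolled set are about 2% to 10% of an assumed 22-point decline. These sizes rest wholly on assumed SDs, correlations and dropout, since the documents supply none. No safety result is touched.

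A reader might also infer that adding the interaction is enough. It is not: with LS means at the baseline mean over observed records, the interaction model was biased as much as or more than the model as written.

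**What to change.** In SAP section 9.2.1.1:

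1. Add BASE*AVISIT to the fixed effects of the MMRM and of the regional subgroup model. If the code already has it, say so and align the text.
2. State that LS means at every visit are evaluated at the mean baseline ALSFRS-R of the full safety analysis population, one value per subject, including subjects with no post-baseline score. Do not use the mean over observed visit records, which gives more weight to subjects who stay longer.

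The cost is three degrees of freedom (four visit-specific slopes in place of one) and no new data. In the n = 140 case the SD of the Week 96 estimate rose from 1.45 to 1.51.
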